## 1.0 TRIAL SUMMARY

[figure not shown]
Abbreviated Title	Pembrolizumab for Relapsed Disease after Allogeneic Hematopoietic Stem Cell Transplant
Trial Phase	Phase 1b
Clinical Indication	Relapsed myelodysplastic syndrome, acute myeloid leukemia and acute lymphoblastic leukemia after allogeneic hematopoietic stem cell transplant
Trial Type	Single center, Investigator-Initiated
Type of control	N/A
Route of administration	IV
Trial Blinding	none
Treatment Groups	Single treatment group
Number of trial subjects	20 subjects
Estimated enrollment period	2 years
Estimated duration of trial	3 years
Duration of Participation	14 months
Estimated average length of treatment per patient	12 months

## 2.0 TRIAL DESIGN

### 2.1 Trial Design

**Single-arm open label phase 1b clinical trial of pembrolizumab (Merck) to determine the feasibility and immunologic correlates for treating relapse of primary malignancy after allogeneic stem cell transplantation.**

### 2.2 Trial Diagram

\* standard induction chemotherapy may be administered during induction at investigators discretion if concern for rapid clinical progression of malignancy (see 5.2.1.2).

† Primary study endpoint (s) are ORR (PR+CR) at day 35 and day 77

## 3.0 OBJECTIVE(S) & HYPOTHESIS(ES)

### 3.1 Primary Objective(s) & Hypothesis(es)

#### 3.1.1 Primary Objectives

- 1) To establish the safety of delivering single agent pembrolizumab ± chemotherapy to patients with relapse of ALL, AML or MDS after allogeneic transplantation.
- 2) To determine the overall response rate (ORR) to single agent pembrolizumab ± chemotherapy in patients with relapsed ALL, AML or MDS after allogeneic transplantation.
- 3) To describe the incidence of Graft vs. Host Disease (GvHD) and/or other clinically significant immune mediated toxicities after pembrolizumab ± chemotherapy.

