#### **Primary objective endpoints:**

Efficacy:

- ORR at days 35 and 77 in subjects receiving pembrolizumab monotherapy
- ORR at day 77 in subjects receiving pembrolizumab  $\pm$  standard induction chemotherapy
- Clinical Benefit Rate (CBR) at days 35 and 77 in subjects receiving pembrolizumab monotherapy

Safety:

- Incidence and severity of GvHD after administration of pembrolizumab
- Grade 3-5 Regimen-related toxicities (RRT) per CTCAE v4
- Incidence of immune mediated toxicities attributable to pembrolizumab

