## **8.0 STATISTICAL ANALYSIS PLAN**

### **8.1 Statistical Analysis Plan Summary**

The statistical plan for this feasibility study of pembrolizumab for relapse after HCT is primarily directed toward the primary objective of safety and feasibility after HCT. The trial will additionally estimate the proportion of patients responding to pembrolizumab monotherapy by overall response rate (ORR). The ORR (CR+PR) will also be estimated at day 35 and 77 for subjects receiving  $\geq$  one dose of single agent pembrolizumab. If progression is noted subjects may receive standard induction chemotherapy. Subjects who are administered standard induction chemotherapy prior to day 77 (for any reason) will be considered non-responders for ORR of pembrolizumab monotherapy. However, we will perform a planned subset analysis to determine the ORR at day 77 for subjects receiving pembrolizumab followed by systemic chemotherapy.

The incidence of grade 3-4 acute GvHD and significant ( $\geq$  grade 3) immune mediated toxicities will be estimated at the conclusion of the treatment period which is 30 days after the last dose of pembrolizumab. Overall survival (OS) and Disease Free Survival (DFS) at 12 months will be calculated by Kaplan Meier methods. The observation period for OS and DFS will begin at the confirmed date of relapse after HCT until death or last scheduled clinical follow up. These observations will assist in determining whether further investigations are warranted after HCT.

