### 8.2.2 Sample size estimate to assess if study drug is promising for further study

Considering the highly refractory nature of the subjects to be enrolled in this study and our lack of understanding of the kinetics of response to pembrolizumab in the post HCT setting, the investigators will be cautious about the potential underestimation of response of this novel agent. In addition, several, but not all patients are expected to receive standard chemotherapy at some point during their on-study therapy, thereby potentially confounding interpretation of the response rate to study drug. Therefore, the following criteria will be used to assess if the study drug is promising for further study:

(a) if  $\geq 4$  subjects demonstrate evidence of clinical benefit the drug will be considered promising. With 20 subjects we would be 90% confident that the true clinical benefit rate (CBR) lies between 7% and 40%. The CBR will be assessed on both day 35 and day 77 as determined by the proportion of subjects who receive pembrolizumab monotherapy who achieve either stable disease (SD) or ORR prior to the addition of standard chemotherapy

(b) the observation of any CRs seen in subjects not receiving standard chemotherapy will be considered promising.

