- All subjects will be inherently at risk for the development of GvHD as this study is limited to patients who have relapsed post-HCT. Although screening will exclude patients with active GvHD requiring immunosuppression, subjects will remain at risk independent of whether they receive study drug. The expected incidence of clinically significant grade 2 to 4 acute GvHD (requiring therapy) without Pembrolizumab is estimated to be 40-50%.
- Patients who relapse (without GVHD present) may still be receiving standard immunosuppression post-HCT to reduce the risk of inciting GVHD. Immunosuppressive medications (IS) may be withdrawn or tapered per usual care. Because patients are at risk for the development of GVHD within several weeks after IS withdrawal tapering may occur during administration of pembrolizumab at a rate determined by the treating physician. Due to timing of IS withdrawal overlapping with the treatment period for pembrolizumab, potentially confounding its relationship to the study drug, an aggregate summary of toxicity will be used to determine whether PD1 blockade is potentially associated with an increase in the severity of acute GvHD.
- For the purposes of this study, toxicity will be deemed as excessive if 12 of 20 subjects (60%) develop severe acute GvHD ( $\geq$  grade 3-4) OR  $\geq$  grade 3 immune related adverse events that do not improve to grade 1 after systemic corticosteroid treatment for 14 days. This study specific stopping rule is intended to capture excessive rates of severe acute GvHD (grades 3-4) as an adverse safety signal. We have set this threshold because some degree of GvHD is an anticipated consequence of usual withdrawal of immune-suppression and chemotherapy which is a current treatment standard for relapse. Grade 2 GvHD is associated with less morbidity and mortality compared to grades 3-4 and may be a potential surrogate of a beneficial anti-leukemic response (GvL), thus grade 2 GvHD will be recorded but not included in the stopping definition. The occurrence of severe acute GvHD for this toxicity rule will be monitored during the induction treatment period until 30 days after the last induction treatment dose of pembrolizumab given for the induction phase (doses 1-4).

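### The primary safety rates are not divided at the start of on-study chemotherapy, although efficacy is, so as planned they describe the whole strategy and not pembrolizumab itself

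*Combined protocol and SAP*

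**What the plan says.** Primary objective 1 in section 3.1.1 reads: "To establish the safety of delivering single agent pembrolizumab ± chemotherapy to patients with relapse of ALL, AML or MDS after allogeneic transplantation". Objectives 2 and 3 are likewise worded as pembrolizumab with or without chemotherapy. The hypothesis in 3.1.2 is narrower: PD-1 blockade will produce responses without excessive GvHD.

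Efficacy is separated by chemotherapy. One primary endpoint is "ORR at days 35 and 77 in subjects receiving pembrolizumab monotherapy". Section 8.1 adds: "Subjects who are administered standard induction chemotherapy prior to day 77 (for any reason) will be considered non-responders for ORR of pembrolizumab monotherapy", and then: "we will perform a planned subset analysis to determine the ORR at day 77 for subjects receiving pembrolizumab followed by systemic chemotherapy". Section 8.2.2 gives the reason: "several, but not all patients are expected to receive standard chemotherapy at some point during their on-study therapy", which it says may confound the response rate.

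Safety has no such separation. The endpoints in 4.2.2.1, repeated in 8.2.1, are "Incidence and severity of GvHD after administration of pembrolizumab", "Grade 3-5 Regimen-related toxicities (RRT) per CTCAE v4" and immune-mediated toxicity attributable to pembrolizumab. The only censoring rule, in 8.2.1, concerns other immune therapies such as DLI; chemotherapy is not named.

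Section 8.2.4 uses an aggregate toxicity summary to judge whether PD-1 blockade increases the severity of acute GvHD. It also says that "some degree of GvHD is an anticipated consequence of usual withdrawal of immune-suppression and chemotherapy which is a current treatment standard for relapse".

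**The concern.** Section 8.2.2 recognises chemotherapy as a confounder of response, and 8.1 handles it there. The same chemotherapy, in the same subjects, can also cause grade 3-5 toxicity, and by the plan's own account it contributes to expected GvHD. A single rate across both periods mixes toxicity under pembrolizumab alone with toxicity after physician-choice chemotherapy.

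Two errors of reading become possible. A high grade 3-5 rate may be blamed on pembrolizumab when much of it followed chemotherapy. Or an early pembrolizumab signal may be put down to chemotherapy. Either would weaken the safety half of the hypothesis in 3.1.2.

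**Working it through.** **1. The plan's own figures.** Section 8.2.4 halts accrual at 6 or more of 10, or 9 or more of 15, with severe acute GvHD. The exact probability of stopping at either look is P(X10 ≥ 6) + Σ(x ≤ 5) P(X10 = x) · P(X5 ≥ 9 − x).

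| True rate | Stated | Recomputed |
|---|---|---|
| 30% | 0.05 | 0.051 |
| 40% | 0.18 | 0.186 |
| 50% | 0.43 | 0.430 |
| 60% | 0.71 | 0.709 |

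The figures are sound for a rate over all subjects. They say nothing about the rate before chemotherapy.

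**2. Is there post-chemotherapy time in the safety windows?** Inputs:
- Dose 2 is on day 22, and the first marrow assessment is around day 35 (section 6.0).
- Chemotherapy before that marrow is discouraged (5.2.1.2).
- Induction pembrolizumab stops once chemotherapy starts, but maintenance is possible if day 77 shows CR or PR (5.2).
- Adverse events are collected to 30 days after the last dose (7.1.2.1, 7.1.4.3). Severe GvHD is counted to 30 days after the last induction dose, and total GvHD to 90 days after the last infusion (8.2.1).

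Take a subject who switches on days 36 to 40 after two doses:
- 30-day window: 22 + 30 = day 52. Post-chemotherapy time is 52 − 40 = 12 to 52 − 36 = 16 days.
- 90-day total GvHD window: 22 + 90 = day 112. Post-chemotherapy time is 112 − 40 = 72 to 112 − 36 = 76 days.
- Subject who enters maintenance at day 85: the treatment period in 7.1.4.3 runs from the first dose to 30 days after the last maintenance dose, so it spans the chemotherapy course.

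**3. What a pooled count leaves open.** Suppose 6 of 20 have an event. The number among subjects never given chemotherapy could be:
- 5 given chemotherapy: 1/15 to 6/15
- 10 given chemotherapy: 0/10 to 6/10
- 15 given chemotherapy: 0/5 to 5/5

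**4. Possible size (assumptions, not plan figures).** Let pm be the proportion with an event on monotherapy, k the number of 20 given chemotherapy, and pc the probability of an in-window event after chemotherapy, independent of the first. Then pooled rate = pm + (1 − pm) · pc · k/20. With pm = 0.20:

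| k | pc | Pooled rate | Pooled / pm |
|---|---|---|---|
| 8 | 10% | 0.20 + 0.80 × 0.10 × 0.40 = 0.232 | 1.16 |
| 12 | 30% | 0.20 + 0.80 × 0.30 × 0.60 = 0.344 | 1.72 |
| 8 | 70% | 0.20 + 0.80 × 0.70 × 0.40 = 0.424 | 2.12 |
| 12 | 70% | 0.20 + 0.80 × 0.70 × 0.60 = 0.536 | 2.68 |

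The documents give none of pm, k or pc, so this is a range of possibilities and not an estimate.

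**5. Precision after a split.** Clopper-Pearson 90% intervals are 14% to 51% for 6/20 and 9% to 61% for 3/10.

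**The case against.** **The objective is the strategy.** Objectives 1 and 3 include chemotherapy, so the all-subjects rate is a proper answer to them. This stands, and the pooled rate should stay. It does not settle the matter, because objective 2 has the same wording and its endpoints are still split, and because 3.1.2 and 8.2.4 go on to speak of PD-1 blockade.

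**Chemotherapy may be mild, and little of its toxicity may count.** Section 5.2.1.2 allows hypomethylating as well as cytotoxic regimens and gives no shares. Section 7.2 makes reporting mandatory for non-hematologic events of grade 3 or higher, so marrow toxicity may not be counted. Both points stand, and they are why the low end of the range above has to be shown.

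**Attribution already handles it.** Table 6 requires a physician's causality judgement for each event, and one endpoint is limited to attributable toxicity. This helps in part. The other two endpoints carry no such limit, and the judgement is made open-label, with chemotherapy available as the alternative cause.

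**Aggregation was deliberate.** Section 8.2.4 aggregates because withdrawal of immunosuppression overlaps with treatment. That confounding exists before chemotherapy too, so a split by date will not isolate a pembrolizumab effect on GvHD. This also stands.

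**A stronger reading to avoid.** A reader might infer that the trial cannot show whether single-agent pembrolizumab is safe, or that the planned rate at least doubles the single-agent one. The documents support neither. Onset dates are recorded, so the limit lies in the planned summary and not in the data, and a doubling needs high assumed event rates after chemotherapy.

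**Conclusion.** The point holds as a gap in the planned summaries. The pooled safety rates answer the objectives as written. They do not by themselves support the plan's further conclusion about PD-1 blockade, and safety lacks the separation that efficacy has.

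The overlap is about 12 to 16 days of the 30-day window for a switch on days 36 to 40. It is longer for total GvHD and for subjects who enter maintenance after chemotherapy. The effect on the rates cannot be derived from the documents; a ratio of about 1.2 to 2.7 rests wholly on the assumed inputs. The stopping rules are not affected. This is an inexpensive improvement to a descriptive 20-subject trial and does not invalidate its design.

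**What to change.** In section 8.2.1, keep the pooled rates, leave the stopping rules in 8.2.4 as they are, and add one descriptive table of the same three endpoints by onset date:

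1. **First dose to chemotherapy start, all treated subjects.** Report with time at risk, or as cumulative incidence with chemotherapy start and death as competing events. Follow-up will be unequal and will be cut mainly in progressing subjects, so a plain proportion can understate toxicity. State that delayed pembrolizumab toxicity, which 5.2.1.2 says can appear weeks after a dose, may fall after the cut.
2. **Chemotherapy start to the first maintenance dose or the end of the safety window,** chemotherapy-treated subjects only.
3. **Maintenance after chemotherapy,** shown separately, because pembrolizumab exposure resumes.

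State that withdrawal of immunosuppression still confounds GvHD in every period.

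Make the chemotherapy start date a required CRF item. Section 5.3.1 leaves dates of medication changes optional, although the day-77 non-responder rule already depends on that date. Adverse event start and stop dates are collected under Table 6.

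The cost is one table and one CRF field. The downside is small numbers with wide intervals (9% to 61% for 3/10), so the table should be read descriptively.

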### 3.1.2 Hypotheses for Primary Objectives

Blockade of PD-1 with pembrolizumab will enhance (induce) the Graft vs. Leukemia (GvL) effect resulting in objective clinical responses without excessive toxicity (GvHD) in patients who experience relapse of primary malignancy after allogeneic transplantation.

## 3.2 Secondary Objective(s) & Hypothesis(es)

### 3.2.1 Secondary Objectives

- 1) Estimate the one-year overall and disease-free survival in patients administered pembrolizumab for relapse after HCT

#### 3.2.1.1 Exploratory Objectives

- 1) Determine the immunologic correlates of response to checkpoint blockade in patients with hematologic malignancies who have relapsed after allogeneic transplantation via assessment of PD1-PDL1 axis with a well-defined focus on T and NK cell phenotypes, functions and leukemia specific responses.
- 2) Determine the antigenic peptide repertoire of relapsed MDS and AML by whole exome sequencing (WES), bioinformatically nominate the most immunogenic antigens from the WES analyses and then functionally validate the top predicted peptides in silico and in vitro.
- 3) Determine if PD-L1 expression at relapse serves as a biomarker for response to pembrolizumab in hematologic malignancies as has been reported in solid malignancies.
- 4) Identify responsive and resistant malignant clones and assess kinetics and depth of response to treatment with ultrasensitive mutation detection (droplet digital PCR [ddPCR] and single-molecule/real-time sequencing [SMRT])

### 3.2.2 Hypotheses for Secondary and exploratory Objectives

Blockade of PD-1 with pembrolizumab can reverse the putative immunobiologic mechanisms reported to play a significant role in contributing to relapse after allogeneic transplantation via the development of 'adaptive resistance' determined by analyses of immune peptide repertoire by WES and specific expression of PD-L1 and other immune inhibitory markers on (Galectin 9, HVEM, CD48, CD155) leukemic cells and characterize the 'senescent/exhausted' CD8/4+ immunophenotype (PD1, LAG3, TIM3).

## 4.0 BACKGROUND & RATIONALE

Allogeneic stem cell transplantation provides the only modality with curative potential for many patients with life-limiting hematologic malignancies, particularly those with acute myelogenous leukemia (AML).

**Relapse After Allo-HCT:** According to the Center for International Bone Marrow Transplant Registry (CIBMTR), approximately 40% of mortality after allogeneic hematopoietic cell transplantation (HCT) occurs from relapse. To our knowledge, there have been no successful approaches for reducing relapse after HCT. In AML, relapse rates range from 25% to 65% depending on HCT and disease specific risk factors including conditioning intensity, T cell depletion, cytogenetic profile and status of disease at the

time of HCT. Refractory or relapsed AML, not in remission at time of HCT, has the highest relapse, approximately 60% or greater.

Management of relapse has been unfortunately met with little success and the proportion of patients with long term survival after relapse HCT remains unacceptably low. Although the use of Donor Lymphocyte Infusion (DLI), often in combination with chemotherapy has become a commonly utilized treatment approach, the long term outcomes remain poor and the incidence of Graft vs. Host Disease (GvHD) after DLI is a significant limitation to its overall success. For example, 13% of patients with AML survived one-year if relapse occurred 6 months after HCT (Bejanyan et al. BBMT 2015).

[figure not shown]
Although multi-factorial, one of the primary mechanisms by which HCT achieves anti-tumor control is via an immune-mediated 'Graft vs. Leukemia' (GvL) effect. The mechanisms by which the host and donor hematopoietic and non-hematopoietic cells and tissues interact to achieve successful disease control and immune surveillance are complex and difficult to study in humans. Over the last decade, there has been extraordinary progress in our understanding of these mechanisms, not only those involved in the activation of the immune effectors to enhance cytotoxicity, but in particular, the numerous pathways involved in inhibition of the immune system that otherwise protect healthy tissues from autoimmune reactions, but can paradoxically lead to immune escape by malignant cells, culminating in clinical relapse. Included among the multiple negative regulatory mechanisms which appear to contribute to the inhibition of sufficiently primed anti-leukemic (tumor) T cell responses are 1) suppression of conventional T-cell function by regulatory T-cells, 2) up-regulation of CTLA-4 on T-cells, 3) tryptophan catabolism by IDO, 4) T-cell anergy due to poor co-stimulation by tumor cells, 5) functional senescence or exhaustion of antigen specific CD8+ T-cells after allotransplantation and 6) engagement of PD-1 on activated T-cells with PD-L1 [Figure 1]. Although interfering with any one of these pathways might enhance the GvT effect, this proposal focuses on the latter via blockade of PD-1 with pembrolizumab in relapsed AML or MDS after HCT.

Several murine and human studies have established that PD-1/PD-L1 interactions play a critical role in immune evasion and provide strong rationale for enhancing GvL via PD-1 blockade post-HCT.

PD-L1 expression has been confirmed in several hematologic malignancies, including AML, providing the rationale for exploring both the impact of PD-1 blockade via pembrolizumab and the correlation of surface expression and response among disease subtypes. In addition, there are no published data exploring Pembrolizumab post allogeneic HCT in which a potentially 'healthy' immune effector system from the donor can be exploited to re-establish immune surveillance and cancer 'immuno-editing'. A unique aspect of this study is that instead of 'activating' autologous T cells from a cancer patient with long-standing exposure to the tumor, the potential target are the 'normal' donor T-cells previously infused (and still persistent) after allogeneic HCT which have potentially become senescent/exhausted. Although there is precedent for the 'inhibition of inhibitory pathways' via CTLA-4 blockade with ipilimumab, suggesting an enhancement in T-cell response against AML without increasing GvHD in the post-HCT setting, this trial will focus on PD-1 blockade via pembrolizumab.

By targeting established immunoregulatory pathways with pembrolizumab, we postulate that we can overcome inhibition mediated by PD-1 binding with PD-L1 and PD-L2, thereby inducing or restoring the immune-mediated GvL effect without undue toxicity in a patient population with very limited treatment options.

When compared to the extensive data regarding the potential role of checkpoint blockade in solid tumors, there has been a relative paucity in hematologic malignancies. This proposal will investigate PD-1 based check-point blockade (pembrolizumab) in the post-HCT setting, and will provide an important 'proof of principle' for understanding key mechanisms of immune escape after HCT, reversal of

senescence/exhausted immunophenotype, and potential impact on re-establishing GvL and leukemic response. If successful, these clinical and laboratory data would provide compelling rationale for further definitive lines of investigation of pembrolizumab in this or related settings.

**FIGURE 1. Immune checkpoint blockade as an immunotherapeutic modality.** T-cell receptor binding to a human leukocyte antigen/peptide complex is a central event in cytotoxic T lymphocyte (CTL) mediated elimination of leukemia cells as it induces an activation signal within the CTL. Immune checkpoints refer to a number of inhibitory pathways that are crucial for maintaining self-tolerance and modulating the duration and amplitude of immune responses in peripheral tissues in order to minimize collateral tissue damage. It is well described that tumors use different immune checkpoint pathways as a major mechanism of immune resistance against leukemia-specific CTL. PD-1 is mainly expressed on antigen-experienced memory T cells in peripheral tissues (effector phase). Leukemia cells use this regulatory mechanism to evade a leukemia-directed CTL response by upregulating PD-L1, which is the ligand for PD-1, on its surface. Blocking monoclonal antibodies (orange squares) directed at the inhibitory immune receptors CTLA-4, PD-1 and PD-L1 have all emerged as promising novel treatment approaches for cancer patients. Figure and caption from MH Andersen, Leukemia 2014.

